9.1.2 Exclusion Criteria

Patients who meet the following criteria may NOT participate in the study.

1. Active infection of bacterial or viral (non-Covid-19) origin

9.2 Patient Identification

Each patient / data is identified by a unique identification code. This code is only used for study purposes for pseudonymization of the data. After informed consent, every person will be given a patient study number/code. The patient code consists of a observational study (Obs) code followed by the patient number (for example, the first patient enrolled would have the following number: XXX-001, second XXX-002, etc.). For the duration of the study and afterwards, only the patient's physician will be able to identify the patient based on the patient identification code.

Patient identification log will be set up to provide the link between the patient and their assigned study number. This document must be stored confidentially only at the Institution / site.

10 DATA COLLECTED DURING THE STUDY

All available data will be captured from medical records that will be generated by the treating physicians as per their standard practice i.e. no GCP requirements will be imposed on the medical records. See Section 10.1.1for information about the data collected that will be collected.

10.1.1 Tabulated Overview

All available data will be captured from medical records. The following data will be recorded (if available):

Laboratory-confirmed COVID-19 (Positive, validated RT-PCR Assay of nasopharyngeal swabs and ideally serum)

Demographics
Prior medications used

Past Medical History

The following data will be recorded from the time of first ventilation for 30 days (if available):

General Information	
Hospital admission	
ICU admission	
Mobility	
Respiratory parameters	
Use of inotropic medication	
RR/MAP	
Rx (X-Thorax, CT scans)	
Fever/rash/abnormal cardiac function	
Mechanical ventilation	
ECMO	
Infectious Disease Parameters	
Inflammatory markers	
Peripheral edema	
Cytokine panel- Full Cytokine panel workup pre and post treatment (Serum)	
Pre-treatment CRP Levels	
Post-treatment CRP Levels /24h	
Cardiac parameters/Oxygen saturation	
General Disease Parameters	
APACHE II score	
Performance status (ECOG/Karnofsky)	

Laboratory Assessments

Virus titer

IL-6 status Pre-treatment Serum IL-6 levels (ELISA or similar approach, e.g.: Multiplex cytokine array)

Extended blood panel (Hb/Ht), thrombocytes, including PMBC

Coagulation status

History of HIV/HHV-8/Hepatitis/Tuberculosis infections

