6 STUDY OBJECTIVES

The is a case control study to observe treatment and collect data on two cohorts of patients treated with siltuximab and a corresponding case control group of patients who have developed severe respiratory complications with COVID-19 infection.

Primary objective

Cohort A: reduction of the need of invasive ventilation or 30-day mortality

Cohort B: reduction of mortality

Secondary objectives

Cohort A

Reduction of the need of time of ventilatory support

Improvement of the lung function

Improvement of radiologic findings

Cohort B

Reduction of days of need of intubation

Percentage of patients that undergo to tracheostomy

Improvement of the lung function

Improvement of radiologic findings

Primary endpoint:

Cohort A: Reduction of the rate of need of invasive ventilation or 30-day mortality

Cohort B: Reduction of length of ICU staying or 30-day mortality

Secondary endpoints:

Cohort A

Reduction of days of need of ventilatory support

Improvement of P/F fraction (resolution of ARDS i.e. P/F>300, or increase from baseline value of at least 50% if P/F>100 or 100% if P/F<100, at day 3, 8 and 15)

Reduction of the duration of invasive ventilation or length of ICU

Improvement of radiologic imaging

Cohort B

Reduction of days of need of intubation

Percentage of patients that undergo to tracheostomy

Improvement of P/F fraction (resolution of ARDS i.e. P/F>300, or increase from baseline value of at least 50% if P/F >100 or 100% if P/F<100, at day 3, 8 and 15)

Improvement of radiologic imaging

Exploratory end points

Correlation of outcomes with IL-6 levels

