8 OBSERVATIONAL PLAN

8.1 Overall Study Design and Plan – Description

This is a single-center, observational case control study in Italy that follows the use of treatment siltuximab in patients diagnosed with COVID-19 infection who have developed serious respiratory complications. Retrospective data collection will be carried out on patients who have received the drug through the compassionate use program. (this program is still ongoing, and enrolling patients).

Patients receiving siltuximab will be included into this observational study and will be divided into 2 cohorts, split in an approximate 3:1 ratio: 75% will be in Cohort A and are not in an ICU setting and are not on mechanical ventilation, while 25% will form Cohort B and consists of patients in an ICU setting who are receiving invasive ventilation.

[figure not shown]
Each patient will be matched to a consented case control receiving treatment other than siltuximab for their condition.

Match Criteria

Patients receiving siltuximab and controls will be matched according to the following criteria:

- Age (by decades)
- Sex (M/F)
- P/F fraction (<100, 100-150 or >150) at baseline
- Antiviral therapy

Figure 1: Study Design

Procedures outlined in this protocol are based on the compassionate use program, where patients are managed as per clinicians' best judgement and best practice. No procedures are required by this observational protocol. Data on the procedures already performed during the routine diagnosis and treatment of COVID-19 patients will be collected. The list of clinical and laboratory parameters is provided to direct data collection for this observational study (as available in the medical records).

During their hospitalization, patients will be monitored as per standard hospital practice or as per national (emergency) guidelines in accordance with extraordinary circumstances relating to the COVID-19 outbreak. After discharge, patients will be asked to provide (from their primary health care providers) relevant laboratory results for 30 days following start of COVID-19 treatment via ventilation (either mechanical or non-invasive).

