9 STUDY POPULATIONS

9.1 Eligibility

9.1.1 Inclusion Criteria

Patients must meet the following criteria to be eligible to participate in the study:

- 1. Clinical and radiological diagnosis of pulmonary infection by COVID-19
- 2. Positive microbiological evidence of SARS-CoV-2 infection
- 3. Diagnosis of acute respiratory distress syndrome clinical panel in accordance with Berlin 2012 criteria
- 4. For Cohort A only: subjects are eligible if they are enrolled and treated within 48 hours from the beginning of NIV or CPAP
- 5. For Cohort B only: subjects are eligible if they are enrolled and treated within 48 hours from the beginning of invasive ventilation

While approving this protocol, it is understood that the RA/IEC have approved collection and analysis of the data from deceased patients with COVID-19. See also protocol section 10.1.2.

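### Recording ends 30 days after first ventilation, so an intubation or ICU stay still running then is cut off sooner the later it began; this unequal cap can distort three duration measures

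*Protocol*

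**What the plan says.** The Synopsis and section 10.1.1 both set the same window for ICU admission, mechanical ventilation and the other clinical items: "The following data will be recorded from the time of first ventilation for 30 days (if available"). Section 8.1 describes the 30-day period for laboratory results after discharge as running "for 30 days following start of COVID-19 treatment via ventilation (either mechanical or non-invasive").

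The cohorts enter at different points. Section 9.1.1 states "For Cohort A only: subjects are eligible if they are enrolled and treated within 48 hours from the beginning of NIV or CPAP", and section 8.1 says of this cohort that "75% will be in Cohort A and are not in an ICU setting and are not on mechanical ventilation". For the other cohort, section 9.1.1 states "For Cohort B only: subjects are eligible if they are enrolled and treated within 48 hours from the beginning of invasive ventilation"; it sets no limit on earlier NIV or CPAP time.

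Section 6 lists duration endpoints without a time limit or a time origin. Cohort A has, among its secondary endpoints, "Reduction of the duration of invasive ventilation or length of ICU". Cohort B has "Reduction of days of need of intubation" as a secondary endpoint, and ICU length of stay as one part of its primary endpoint. The matching factors in section 8.1 are age, sex, baseline P/F and antiviral therapy. Section 11.2.3 leaves endpoint analysis to descriptive and exploratory methods and rules out statistical comparison of the groups.

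**The concern.** The clock for data collection starts at first ventilation of any kind, but the durations of interest start at intubation or ICU admission. For a stay that outlasts the window, the recorded length depends on when it began as well as on how long it lasted.

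In Cohort A, the timing of intubation may itself respond to treatment. If siltuximab postponed some intubations without shortening them, long episodes would be recorded as shorter in the treated group. In Cohort B, days on CPAP before intubation are not matched, so the cap may differ between treated patients and controls.

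The limit lies in what is collected. A statistical analysis plan could treat cut-off stays as censored, but it could not recover days that were never recorded.

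**Working it through.** **Inputs from the protocol.** Window: 30 days from first ventilation (Synopsis, 10.1.1). Cohort A starts on NIV or CPAP and is not intubated at entry (8.1, 9.1.1), so any intubation falls on a later day k. In Cohort B, k is the time on NIV or CPAP before intubation, and k = 0 if intubation was the first ventilation. The protocol gives no sample size calculation and no duration figure to reproduce.

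**The cap.** With true duration D, recorded duration = min(D, 30 − k). For ICU days, k is the day of ICU admission, which need not be the day of intubation.

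| True duration | k = 2 | k = 7 | k = 10 | k = 14 |
|---|---|---|---|---|
| 10 days | 10 | 10 | 10 | 10 |
| 20 days | 20 | 20 | 20 | 16 |
| 25 days | 25 | 23 | 20 | 16 |
| 35 days | 28 | 23 | 20 | 16 |

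Only episodes that pass day 30 lose days. With a window of 30 days from intubation instead, the 35-day episode would be recorded as 30 days whatever k is.

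**Effect on the mean (assumption: D lognormal with median m and log-SD σ, unaffected by k).** With c = 30 − k and z = ln(c/m)/σ,

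E[min(D, c)] = m·exp(σ²/2)·Φ(z − σ) + c·[1 − Φ(z)].

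- m = 15, σ = 0.8, k = 2 (c = 28): 20.66 × 0.492 + 28 × 0.218 = 16.26 days.
- m = 15, σ = 0.8, k = 12 (c = 18): 20.66 × 0.284 + 18 × 0.410 = 13.24 days. Fall: 3.02 days. Share cut off: 22% rising to 41%.
- m = 10, σ = 0.8, k = 2 (c = 28): 13.77 × 0.687 + 28 × 0.099 = 12.23 days.
- m = 10, σ = 0.8, k = 7 (c = 23): 13.77 × 0.595 + 23 × 0.149 = 11.62 days. Fall: 0.61 days.

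(Products use unrounded terms.)

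**Sensitivity.** Same formula:

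| Median | log-SD | Intubation day | Fall in mean (days) |
|---|---|---|---|
| 15 | 0.8 | 2 to 5 | 0.7 |
| 15 | 0.8 | 2 to 7 | 1.3 |
| 15 | 0.5 | 2 to 12 | 2.1 |
| 15 | 1.0 | 2 to 12 | 3.4 |
| 8 | 0.8 | 2 to 12 | 1.0 |
| 20 | 0.8 | 2 to 12 | 4.4 |

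With exponential or gamma (shape 2) durations and a shift from day 2 to day 10, the fall is 0.1 to 0.3 days at a true mean of 7 days, 1.2 to 1.5 at 14 days and 2.6 to 2.7 at 21 days.

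**Effect on the median.** The recorded median moves only if the cap falls below the true median. At a median of 15 days and caps of 28 and 18, it is 15 in both cases. In the exponential and gamma runs (day 2 to day 10) it is unchanged for true means of 7 to 21 days, and it falls only for the gamma with mean 28 (23.5 to 20.0).

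**Which endpoints are exposed.**
- Cohort A, invasive ventilation or ICU duration: yes, and a delay of intubation can act through treatment.
- Cohort A, primary endpoint: no; it is not a duration.
- Cohort A, days of ventilatory support: support starts when the window starts, so all patients share one 30-day cap.
- Cohort B, ICU length and days intubated: yes, where CPAP came first.

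**The case against.** The strongest case against the point has four parts.

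**The clock may not start at NIV.** The wording that covers both mechanical and non-invasive ventilation is attached to laboratory results after discharge, so applying it to the clinical data in section 10.1.1 is an inference. It is a strong one: Cohort A has no other ventilation at entry.

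**No rule says that cut-off stays count as complete.** A reader might infer from section 11.2.1.1 that durations will be summarised as plain means of recorded days. The protocol does not say so. That section falls under 11.2.1, on baseline data, and endpoints are governed by 11.2.3, which fixes no method. Censoring would be compatible with it. This part of the objection stands. What remains is that the window does not guarantee an end date for a stay that outlasts it.

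**The mechanism is narrower than it looks.** A reader might infer that any delay of intubation shows up as fewer days, or that siltuximab could produce this in both cohorts. Neither holds. Episodes that end inside the window keep their full length, and Cohort B patients are already invasively ventilated when treated. In Cohort B only an imbalance in earlier CPAP time can act, and the documents give no figure for it.

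**The study is descriptive and small.** About 25 treated patients split 3:1 give some 19 and 6 (25 × 0.75 = 18.75; 25 × 0.25 = 6.25), and no formal comparison is planned. That limits the consequence but does not remove it: section 8.2 includes controls to allow direct comparison, and section 11 plans a descriptive one. In a group of 6, a single 35-day stay recorded as 20 rather than 28 days moves the mean by 8/6 = 1.3 days.

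**Conclusion.** The point holds in limited form. For stays still running 30 days after first ventilation, recorded invasive-ventilation or ICU days are capped at 30 minus the starting day. The cap is unequal between patients in one secondary endpoint of Cohort A, and in Cohort B's ICU length and days intubated unless intubation was the first ventilation.

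The size cannot be fixed from the protocol. Under a lognormal with log-SD 0.8 it runs from about 0.6 days in the mean (median 10, day 2 versus day 7) to 3.0 days (median 15, day 2 versus day 12). The larger figure needs a ten-day shift of every intubation in one group. Shorter stays or smaller shifts give less, longer stays give more, and the median often does not move. These figures assume that true duration does not depend on the day of intubation.

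It would go too far to conclude that the duration objectives cannot be answered. Cohort A's only duration objective is time on ventilatory support, which has a common cap, and Cohort A's primary endpoint is untouched.

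**What to change.** In the Synopsis and section 10.1.1:

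- Keep the 30-day limit for mortality.
- Record start and stop dates of NIV/CPAP, invasive ventilation and ICU stay, from the same hospital's records, until discharge or death.
- State that the invasive-ventilation and ICU duration endpoints are counted from the start of invasive ventilation or from ICU admission.
- Flag any stay still open at data cut as censored, not completed.

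The cost is a few more dates per patient and no added procedure. The downside is a slightly later data lock for patients with long stays.

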10.1.2 Enrollment/Initial Visit

Once a potential patient is identified for inclusion in the observational case control study, the physician will inform the patient about the study. This will include discussing the consent form and asking the patient, if possible, to read and provide consent. Where patient is able to provide only verbal consent (e.g. due to technical reasons, isolation) this consenting will be documented by the doctor who will complete the appropriate paperwork. When the patient is not able to provide consent due to their medical condition, consent for data collection / analysis will given by the doctor.

As COVID-19 is a highly contagious and easily transmissible virus, written consent may not be able to be sought from patients at enrollment. In the interests of human safety, in such circumstances only physicians will sign the informed consent, documenting in the doctor's emergency consent form also the circumstances under which consent was obtained.

Retrospective signed informed consent will be sought from patients when they are clear of the virus and no longer considered to have the potential to transmit COVID-19.

Once at least the doctors emergency consent form is available / there is basis for starting patient data collection and analysis, the physician or a delegate will use a CRF to document the patient's data. Data collection, regardless of type of contact, will follow a standard format and will be conducted equally for all patients.

10.1.3 Demographics

For demographic assessment, the following parameters will be recorded:

- Year of birth
- Gender

10.1.4 History of COVID-19 and Date of Diagnosis (Prior to Start of Treatment, if any)

- Virus Titer
- Positive, validated RT-PCR
- Assay of nasopharyngeal swabs
- Serum

• Other symptoms

10.1.5 Medical History and Concomitant Diseases

Medical history findings (i.e., previous diagnoses, diseases, surgeries, and conditions) meeting all criteria listed below will be collected:

- Not pertaining to the study indication
- Considered relevant to the study

10.1.6 Concomitant Medication

Information on concomitant medication to be collected includes:

- Trade name or International Non-proprietary Name (INN)
- Start date
- Stop date or "continued"
- Daily dose, if applicable

10.1.7 Treatments

All treatments prescribed for COVID-19 and/or COVID-19 symptoms

- Trade name or INN and manufacturer
- Start date
- Stop date or "continued"
- Daily dose, if applicable

10.1.8 Signs and Symptoms

- Laboratory parameters (all laboratory parameters must include the value, the reference range [if available], and whether the value was considered Low or High [if available])
- Hospital admission
- ICU admission
- Mobility
- Respiratory parameters

- Use of inotropic medication
- RR/MAP
- Rx (X-Thorax, CT scans)
- Fever/rash/abnormal cardiac function
- Mechanically ventilated
- ECMO
- Infectious Disease Parameters
- Inflammatory markers
- Peripheral edema
- Cytokine panel full cytokine panel workup pre and post treatment (serum)
- Pre-treatment CRP Levels
- Post-treatment CRP Levels /24h
- Cardiac parameters/Oxygen saturation
- General Disease Parameters
- APACHE II score
- Performance status (ECOG/Karnofsky)
- Laboratory Assessments
- Virus titer
- IL-6 status: pre-treatment serum IL-6 levels (ELISA or similar approach, e.g.: multiplex cytokine array)
- Extended blood panel (Hb/Ht) thrombocytes, including PMBC
- Coagulation status
- History of HIV/HHV-8/Hepatitis/Tuberculosis

10.2 Adverse Events

All SAE related to treatment with siltuximab during Compassionate Use should be reported as per the Compassionate Use Protocol (CUP). If during this study/retrospective data collection it is identified that the SAE's related to siltuximab treatment in COVID-19, or

associated with the disease recorded in the patient records, have not been reported, these must be reported within 24 hours as per the process in the CUP. Follow-up of all SAE's must be completed as per the CUP.

All non-serious AEs related to siltuximab treatment in COVID-19, or associated with the disease recorded in the patient records must be included in the CRF. For each AE, the severity, duration, action taken, and outcome of the event, will be documented in the CRF, if the information is available.

The Investigator will be responsible for reporting all relevant cases to the Regulatory Authorities and Ethics Committee under the CUP.

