5.1 Study Rationale

There is an emergency situation regarding treating patients with COVID-19 and especially those with lung complications and/or acute respiratory distress syndrome (ARDS), which is the main cause of morbidity and mortality in these patients. Siltuximab (SYLVANT) 400 mg is an approved product and dosage for idiopathic Multicentric Castleman Disease (iMCD): it is not indicated for the treatment of COVID-19 infection. However, due to observed clinical (lung dysfunction) and laboratory (high IL-6) presentation in COVID-19 patients, siltuximab (an IL-6 blocker) may potentially benefit patients who developed respiratory complication.

As siltuximab is being used for the first time in this indication, there is a requirement to collect and analyze efficacy and safety data from both the standard of care and siltuximab

treated patients in order to assess risk/benefit as well as the dosing regimen of siltuximab in this patient population. As this is an observational case control study, only available data will be collected and analyzed.

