11.2.4 Analysis of Safety Data

Adverse Events and Serious Adverse Events will be reported using descriptive statistics.

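### Section 10.2 captures adverse events by attributed cause and sends SAEs to the compassionate-use system, so AE and SAE tables would be only partly comparable between siltuximab patients and controls

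*Protocol*

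**What the plan says.** **Capture of non-serious events.** Protocol section 10.2: "All non-serious AEs related to siltuximab treatment in COVID-19, or associated with the disease recorded in the patient records must be included"; the place of entry is the CRF. The next sentence lists the details to document for each AE, if available.

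**SAEs.** Section 10.2 sends siltuximab-related SAEs to the CUP. Unreported SAEs uncovered during data collection, whether siltuximab-related or disease-associated, take the same route; the text on the latter reads "associated with the disease recorded in the patient records, have not been reported, these must be reported within 24 hours as per the process in", and CUP is the process it names. It adds: "Follow-up of all SAE's must be completed as per the CUP".

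**Controls.** Section 8.1: "Each patient will be matched to a consented case control receiving treatment other than siltuximab for their condition".

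**Purpose.** Section 5.1 says "there is a requirement to collect and analyze efficacy and safety data from both the standard of care and siltuximab" treated patients, so that risk and benefit can be assessed. Section 8.2 gives direct comparison, including on safety, as the reason for having a matched control group. Section 10.1.2 says that data are collected in one standard way for all patients.

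**Analysis.** Section 11 plans a descriptive treated-versus-control comparison within each cohort, covering endpoints and other measurements. Section 11.2.4: "Adverse Events and Serious Adverse Events will be reported using descriptive statistics".

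**The concern.** A side-by-side AE table can be read only if an event of a given kind has the same chance of entering it in either group. Section 10.2 makes entry depend on what the event is attributed to, and one of its two qualifying attributions exists only in the siltuximab group. The physicians making that attribution know the treatment. For SAEs, the only stated route is a programme for siltuximab recipients.

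At stake is the reading of the safety summary. A higher AE count under siltuximab could come from the capture rule alone. A control SAE count could be low because no one was told to record those events, not because few occurred. With no formal testing planned, the descriptive counts are the AE evidence that the study will offer. An analysis plan written later cannot recover events that were never abstracted.

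**Working it through.** The protocol states no AE rate, power or other figure to reproduce on this point. The main check is to apply the text of section 10.2 to each class of event.

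**Step 1. What the rule requires, by group**

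| Event class | Siltuximab patient | Control patient |
|---|---|---|
| Non-serious, disease-associated | CRF entry required | CRF entry required |
| Non-serious, caused by siltuximab | CRF entry required | Cannot occur |
| Non-serious, caused by another treatment, not disease-associated | Not required | Not required |
| Non-serious, neither drug- nor disease-related | Not required | Not required |
| SAE | CUP reporting and follow-up; CRF entry not expressly required | CUP is the only route named, and controls are outside that programme; CRF entry not expressly required |

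Only the first row is symmetric and complete. The second and third rows together are the asymmetry for non-serious events: the effects of the drug under study are captured, and the effects of what controls received in its place are not. The fourth row is symmetric, but incomplete in both groups. In the last row, the catch-up sentence on unreported disease-associated SAEs is not expressly limited to treated patients, but the process it names is still the CUP.

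**Step 2. Against the stated purpose.** Sections 5.1 and 8.2 want safety data from both groups for direct comparison, section 10.1.2 says collection is equal, and section 11 plans a descriptive comparison. Section 10.2 delivers this for the first row only.

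**Step 3. Illustration of size.** The planned maximum is 50 patients, half of them treated (Synopsis, Number of Patients): 50 × 0.5 = 25 per group. Let

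- p = share of patients with a disease-associated non-serious AE;
- q = share with a non-serious AE caused by the treatment (siltuximab, or the control's own treatment) and not disease-associated.

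Both are set equal in the two groups, so the true burdens are identical. Taking the two kinds of event as independent, and only required events as recorded:

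- siltuximab group captured: 1 − (1 − p)(1 − q)
- control group captured: p
- artificial difference: q(1 − p)

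| p | q | Siltuximab | Control | Difference |
|---|---|---|---|---|
| 0.6 | 0.1 | 0.64 (16.0/25) | 0.60 (15.0/25) | 4 points |
| 0.4 | 0.2 | 0.52 (13.0/25) | 0.40 (10.0/25) | 12 points |
| 0.2 | 0.3 | 0.44 (11.0/25) | 0.20 (5.0/25) | 24 points |

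Over p = 0.2 to 0.6 and q = 0.1 to 0.3 the difference runs from 4 to 24 points. These values are assumptions; none comes from the protocol. The direction follows from the rule whenever q > 0 and p < 1. Under one rule that ignores cause, the difference is 0 for any p and q.

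**The case against.** **The disease limb covers controls.** This stands. One might read section 10.2 as capturing siltuximab reactions only. It does not, and disease-associated non-serious events can be compared.

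**The rule is a minimum.** This also stands. The text says which events must be entered and forbids no others, and the sentence on details for each AE could be read to include SAEs. But abstractors filling a CRF from charts will tend to follow the stated requirement, and anything recorded beyond it would depend on individual habit.

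**Serious outcomes are collected anyway.** Largely true. Thirty-day mortality and invasive ventilation are endpoint components. ICU admission, ECMO, inotropes and laboratory and coagulation data are on the list for all patients, if available. A reader might infer that serious events in controls go unseen, or that the risk/benefit aim cannot be met. The documents support neither: the medical record is the source for both groups, and these items carry no causality filter. What is missing is an explicit rule for recording SAEs as such.

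**The comparison is modest.** Section 6 lists no safety endpoint, section 11.2.4 does not say by group, and section 11.2.3 rules out statistical comparison of endpoints. The comparative intent has to be taken from sections 5.1, 8.2 and 11. That limits the severity, but unequal capture distorts a descriptive table too.

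**The CUP and CRF are not at hand.** The CRF may hold SAE fields, and CUP records may feed the study tables. That could settle the matter for treated patients. It would give controls an equivalent only if the CRF asks for SAEs in both groups, which section 10.2 does not say.

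**Small numbers limit any safety reading.** True, but this is a separate matter. An upper bound on an event rate when none is seen in 25 patients describes the sample size and would be the same after the fix.

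**Conclusion.** The point holds in a limited form. As written, section 10.2 gives AE and SAE counts that are not comparable between groups, except for disease-associated non-serious events. This conflicts with sections 5.1, 8.2, 10.1.2 and 11. There are three reasons: the siltuximab limb has no counterpart for events from control treatments, other non-disease events are required in neither group, and SAEs are tied to a programme that controls are not in, without an express instruction to enter them in the CRF.

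The direction of the distortion in non-serious AEs is an apparent excess under siltuximab. Its size is unknown; the 4 to 24 points rest on the assumed p and q, on independence, and on abstractors recording only what is required. For SAEs the documents do not allow even an illustration, because the CUP and CRF are not shown.

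Mortality, ventilation, ICU and laboratory data are collected on the same terms in both groups, and no stated endpoint is affected. This should be fixed; it does not undermine the study as a whole.

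**What to change.** Amend section 10.2 and the CRF so that:

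- every AE and SAE found in the medical record is entered in the CRF of both groups, regardless of seriousness or judged cause;
- the period is the one the protocol already uses in section 10.1.1, 30 days starting at first ventilation;
- causality is a separate field and not a condition for entry;
- in treated patients, onset is marked as before or after siltuximab, since the drug may be given up to 48 hours after the qualifying ventilation begins.

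In section 11.2.4, state that all-cause AEs and SAEs are tabulated by group within cohort. Leave CUP reporting and follow-up unchanged.

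The cost is a change of wording, some CRF fields, and somewhat more chart abstraction for up to 50 patients. If that is not feasible, the alternative is to withdraw the comparative safety purpose from sections 5.1 and 8.2 as far as AEs and SAEs are concerned, and to present those events for the siltuximab group only.
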